NON-INTERVENTIONAL (NI) STUDY PROTOCOL

Study information

Title	Registry-based non-interventional analysis of advanced/metastatic renal carcinoma treatment patterns and outcomes in the Hospital district of Southwest Finland.
Protocol number	A4061098
Protocol version identifier	Version 1
Date	28 March 2022
Active substance	axitinib, ATC-code L01EK01 (previously L01XE17) sunitinib, ATC-code L01EX01 (previously L01XE04)
Medicinal product	Inlyta; Sutent
Research question and objectives	The aim of the study is to describe the characteristics, treatment pattern and outcomes of patients with advanced/metastatic renal cell carcinoma (RCC) with medical records in the HDSF data lake. The treatment sequence of mRCC patients and treatment outcomes (overall survival, time-to-next treatment) will be analysed with regard to individual risk score of the patient and over time. In addition, comorbidities, procedures and healthcare usage will be analyzed. As an exploratory objective, the coding practices especially with regard to risk score calculation are assessed.
Author	PPD [REDACTED], PhD, PPD [REDACTED] [REDACTED] email: PPD [REDACTED] tel. PPD [REDACTED]

PFIZER CONFIDENTIAL

[REDACTED]

TABLE OF CONTENTS

1. TABLE OF CONTENTS.....	2
2. LIST OF ABBREVIATIONS.....	4
3. RESPONSIBLE PARTIES	5
4. AMENDMENTS AND UPDATES.....	6
5. MILESTONES.....	7
6. RATIONALE AND BACKGROUND.....	7
7. RESEARCH QUESTION AND OBJECTIVES	9
7.1. Primary objectives	9
7.2. Secondary objectives.....	9
7.3. Exploratory objective	10
8. RESEARCH METHODS	11
8.1. Study design	11
8.2. Setting.....	11
8.2.1. Inclusion criteria	12
8.2.2. Exclusion criteria	13
8.2.3. Patient stratification	13
8.3. Variables.....	14
8.4. Data sources	16
8.5. Study size	17
8.6. Data management	17
8.7. Data analysis	18
8.7.1. Patient characteristics	18
8.7.2. Treatment patterns and treatment lines.....	19
8.7.3. Treatment outcomes.....	20
8.7.4. Morbidity	21
8.7.5. Healthcare resource utilization	21
8.7.6. Changes in coding practices over time	22
8.8. Quality control.....	22
8.9. Limitations of the research methods	22
8.10. Other aspects	23

9. PROTECTION OF HUMAN SUBJECTS	23
9.1. Patient information	23
9.2. Patient consent	23
9.3. Institutional review board (IRB)/Independent ethics committee (IEC)	23
9.4. Ethical conduct of the study	23
10. MANAGEMENT AND REPORTING OF ADVERSE EVENTS/ADVERSE REACTIONS	23
11. PLANS FOR DISSEMINATING AND COMMUNICATING STUDY RESULTS.....	24
12. REFERENCES	24
13. LIST OF TABLES	25

1. LIST OF ABBREVIATIONS

[figure not shown]
Abbreviation	Definition
AJCC	American Joint Committee on Cancer
ATC	Anatomic therapeutic chemical classification system
BMI	Body mass index
HCRU	Healthcare resource utilization
HDSF	Hospital District of Southwest Finland
HTA	Health Technology Assessment
ICD-10	International Classification of Diseases 10th revision
ICMJE	International Committee of Medical Journal Editors
IMDC	International Metastatic RCC Database Consortium
LOT	Line of treatment
mRCC	(Advanced/)metastatic RCC
OS	Overall survival
PFS	Progression free survival
PO	Primary objective
RCC	Renal cell carcinoma
RWE	Real-world evidence
RWD	Real-world data
SAP	Statistical analysis plan
SO	Secondary objective
SoC	Standard-of-Care
TKI	Tyrosine kinase inhibitor
TNM	Tumor – Node – Metastasis (classification of malignant tumors)
TTNT	Time to next treatment
VEGFR	Vascular endothelial growth factor receptor

3. AMENDMENTS AND UPDATES

None.

PFIZER CONFIDENTIAL

4. MILESTONES

Milestone	Planned date
Auria permission and start of data collection	01-May-2022
End of data collection	31-May-2022
The following milestones are dependent on data set completion date. The planned dates have been estimated based on data completion by the end of May 2022:	
Data analyses	01 September 2022
Final study report	01-Nov-2022
Publication submission	To be determined

5. RATIONALE AND BACKGROUND

Renal cell carcinoma (RCC) is among the 10 most frequently occurring cancers and the most common type of kidney cancer occurring in Western communities [1]. RCCs comprise a heterogeneous group of malignant neoplasms arising from the nephron. Risk factors for RCC include obesity, hypertension, cigarette smoking, diet, diabetes, and male gender [1].

After decades of increasing trends in RCC incidence and mortality rates, it seems that rates are stabilising or starting to decline in many Western countries [1]. The worldwide number of kidney cancer cases was 431,288 (62.9% male) and deaths 179,368 (64.4% male) in 2020 [2]. Kidney cancer is more common in males compared to females. The incidence was 7.8 and mortality 3.0 per 100,000 males in high human development index countries in 2020 [2]. In Finland, the number of new kidney cancer cases was 635 in males and 353 in females in 2019 [3], and the number of prevalent patients was 4,943 males and 3,867 females in 2019 according to the Finnish Cancer Registry [4].

Localized RCC can be curatively treated with nephrectomy. However, about 20–30% of patients present with metastatic RCC (mRCC) at the time of diagnosis [5]. In addition, another 20% of patients with localized RCC undergoing nephrectomy will have a relapse and develop mRCC during follow-up. Despite the recent advances in mRCC treatment, metastatic disease is often fatal [6].

[figure not shown]
Over the last decade, the treatment of advanced/metastatic RCC has been constantly evolving, especially in the last 2-3 years with the emergence of several novel treatment options in rapid succession. Current recommendations for first-line therapy of mRCC include several combination treatments, superseding the previously recommended antiangiogenic agent monotherapies. The novel options combine an anti-PD-1-antibody with either an antiangiogenic drug (vascular endothelial growth factor receptor (VEGFR) tyrosine kinase inhibitor (TKI)), or an anti-CTLA-4-antibody. The combination treatments are recommended

variably according to the patient's IMDC (International mRCC Database Consortium) risk score. IMDC represents a large collection of real-world data (RWD) on patients with advanced kidney cancer treated with targeted therapies [7,8]. IMDC combinations available for favourable risk patients include pembrolizumab + axitinib, nivolumab + cabozantinib and pembrolizumab + lenvatinib; for intermediate or poor risk patients the combination of ipilimumab and nivolumab is recommended in addition to the aforementioned three combinations. None of the recommended first-line treatment options have been compared head-to-head but all of the pivotal clinical studies have sunitinib monotherapy as a control, a former standard-of-care (SoC). The current second and later line treatment recommendations include VEGFR-TKI monotherapies, such as pazopanib and sunitinib, but will likely be reshaped in the coming years as clinical evidence on the optimal treatment sequence is accumulated.

The prognostic model constructed by the IMDC has been used to stratify patients in contemporary clinical trials and to provide risk-directed treatment selection in everyday clinical practice. The IMDC prognostic model contains six independent predictors of poor survival, which are: Karnofsky performance status of less than 80%, less than 1 year from diagnosis to treatment, anaemia (haemoglobin concentration <lower limit of normal), hypercalcaemia (corrected calcium concentration >upper limit of normal), neutrophilia (neutrophil count >upper limit of normal), and thrombocytosis (platelet count >upper limit of normal). An IMDC risk score is determined for a patient according to the number of poor prognostic factors the patient has; favourable risk patients have 0 factors; intermediate risk patients have one or two factors; and poor risk patients have three or more factors.

In Finland, the mRCC treatment landscape has been shaped by the access and reimbursement status of medications. Here, publicly funded medicines are processed via two different access and reimbursement processes based on the route of administration: outpatient or oral medicines (patient acquires medicine with a prescription from the pharmacy) and hospital medicines (medicines administered at hospital, mainly intravenous medicines). For oral medicines, the Finnish Social Insurance Institution (Kela) reimburses the patient for the costs of outpatient medicines if the Pharmaceuticals Pricing Board (Hila) has confirmed the reimbursement of the medicine. For oral drugs, the marketing authorization holder is responsible for applying for reimbursement. The Finnish Medicines Agency (Fimea) is the national competent authority for regulating pharmaceuticals. Fimea is responsible for initiating the evaluation of hospital medicines to be used in Finland, and makes the initial health technology assessment (HTA). This HTA-evaluation is not made automatically for all new pharmacotherapies or indication extensions, but at the discretion of Fimea. Hospital medicines assessed by Fimea are further assessed by the Council for Choices in Health Care in Finland (COHERE Finland) to issue recommendations on services that should be included in the selection of public health services. Hospital medicines are paid by the municipalities that fund the hospital districts. The use of hospital medicines and prices may also vary greatly from region to region. Use of combination treatments is often problematic due to the Finnish reimbursement system because the combination partners may fall under different processes (eg. a combination of an oral drug and an intravenously administered drug).

PFIZER CONFIDENTIAL

Finland has equal healthcare which is primarily funded by taxation. Thus, all permanent residents in Finland are entitled to public healthcare at a uniform level regardless of their financial situation. Finnish registries cover all individuals living in Finland and no patients are excluded from our study based on their social status or financial capability. In addition, health record data available via data lake technology enable extraction and analysis of large data sets including RWD on disease-related clinical and molecular characteristics and a number of medical procedures. Data for this study will be retrieved from the data lake of the Hospital District of Southwest Finland (HDSF). With a total of 470,000 residents and about 200,000 patients each year, HDSF is one of the biggest hospital districts in Finland.

The aim of this retrospective study is to investigate treatment patterns and outcomes of patients with advanced/metastatic RCC treated at the HDSF. In this protocol, mRCC refers to advanced and/or metastatic RCC. In addition, coding practices of related data and characteristics of all RCC patients will be reported. To our knowledge, this will be the first study to utilize regional Finnish data to characterize RCC patients, and investigate the treatment of the mRCC patient population. The resulting real-world evidence (RWE) is likely to be of interest for the national and global RCC scientific communities.

6. RESEARCH QUESTION AND OBJECTIVES

The objective of this study is to describe the characteristics and treatment outcomes of patients with advanced/metastatic RCC with medical records in the HDSF data lake. In the first primary objective, all RCC patients (with local or metastatic disease) are analyzed (treated and non-treated mRCC patients separately). In all other objectives, only treated mRCC patients will be analyzed. The objectives of the study are to:

6.1. Primary objectives

1. Characterize patients with RCC and with advanced/metastatic RCC (treated and non-treated separately) including e.g. demographics and IMDC risk score.
2. Define treatment patterns and treatment sequences in mRCC.
3. Assess outcomes by treatment line and from diagnosis
 - a. Progression free survival (via proxies such as time-to-next treatment)
 - b. Overall survival
 - i. time to event analyses
 - ii. Cox models

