6.2. Secondary objectives

1. Assess morbidity of metastatic RCC including
 - a. co-diagnoses and procedures
 - b. infections and antibiotic use
 - c. antihypertensive use before and after mRCC diagnosis, as applicable

2. Assess speciality care healthcare resource use (absolute, per patient, per patient year)
 - a. cumulatively over time from diagnosis
 - b. by treatment line

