7. RESEARCH METHODS

7.1. Study design

This is a retrospective registry-based cohort investigation, utilizing existing data generated during routine clinical practice and available in the Hospital District of Southwest Finland HDSF data lake. All adult patients (age ≥ 18 years) with RCC diagnosis (C64*; '*' indicates any number) will be identified from the data lake of HDSF.

The main purpose of this study is to characterize the patient population of advanced/metastatic RCC, and their treatment patterns and treatment outcomes using medical records retrieved from HDSF data lake. The main patient stratification will be the IMDC risk category (see 8.2.3 Patient stratification). Patients with unknown risk score will be analyzed as an own patient group.

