7.2. Setting

The target population of this study is adult patients with RCC and medical records available at HDSF data lake. Estimated number of patients in this study is 220-550. The inclusion criteria is a diagnosis of renal cell carcinoma (ICD-10: C64) between January 2010 and December 2021 (Figure 1). Advanced/metastatic disease stage (mRCC) will be assessed based on ICD-10 diagnosis code for metastasis (C77*-C79*), American Joint Committee on Cancer (AJCC) stage 4, visit to oncologist (specialty code 65), or initiation of treatment for mRCC.

[figure not shown]

Figure 1. Graphical illustration of study time windows and corresponding analyses.

The data collected has been generated as part of standard clinical care, treatment, and follow-up of patients with RCC. In accordance with the Finnish Act on Secondary Use of Health and Social Data 552/2019 (in Finnish: Laki sosiaali- ja terveystietojen toissijaisesta käytöstä), health registry data can be processed in scientific studies without patient consent. The purpose of this act is to establish conditions for the effective and secure processing of, and access to, personal health and social data for certain secondary purposes, such as research and statistics, innovation and development, knowledge management, teaching and authority planning. Thus, the Secondary Act creates a clear legal basis for the use of such registered data for research and innovation related to, for example, the health and well-being of citizens, the prevention of

disease and the development of new treatment methods. This relatively new legislation is also a welcome unification of the fragmented Finnish national rules regarding the use of healthcare and social welfare data. In addition, it takes into consideration current data protection requirements.

In the primary objective 1 (characteristics), all RCC patients will be analysed (local and metastatic diseases separately), while in the other objectives only treated mRCC patients will be analysed. Therefore, there are two cohorts to be analysed: 1) characteristics cohort (including all RCC patients), 2) mRCC cohort (including only treated mRCC patients).

Definitions for mRCC cohort

Index: Date of the first mRCC diagnosis; date of the metastatic disease identified as first of the following after the initial RCC diagnosis

- ICD-10 diagnosis code (C77*-C79*) for metastatic disease
- AJCC stage 4
- Visit to oncologist (specialty code 65) with RCC as main diagnosis

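### Overall survival has two possible start dates in the text, and counting it from mRCC diagnosis in a treated-only cohort would build in guaranteed survival time

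*Combined protocol and SAP*

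**What the plan says.** - **Objective.** Section 6.1, third primary objective: "Assess outcomes by treatment line and from diagnosis". It covers both PFS (through TTNT) and OS, and does not say whether the initial RCC or the mRCC diagnosis is meant.
- **General index.** Section 7.2, for the mRCC cohort: "Index: Date of the first mRCC diagnosis". This is the earliest of a metastasis code, AJCC stage 4, an oncologist visit or the start of mRCC treatment.
- **Override.** The same section then moves the index to the start of treatment when treatment outcomes are analysed. The Study information table counts OS as one of these: "treatment outcomes (overall survival, time-to-next treatment".
- **Analysis.** Section 7.7.3, headed Treatment outcomes, runs OS from index without saying which index, and gives OS by line a separate rule (start of each line). PFS/TTNT runs only from the start of the current line. Cox models are to correspond to these analyses.
- **Population.** Section 6, after the first primary objective: "In all other objectives, only treated mRCC patients will be analyzed". Sections 7.2 and 7.2.2 repeat the restriction.
- **Strata.** Section 7.1: "The main patient stratification will be the IMDC risk category". Section 7.2.3 fixes the category at first treatment for mRCC, and its first risk factor is an interval under one year from RCC diagnosis to that treatment.
- **Limitations.** Section 7.9 does not mention that results are conditional on receiving treatment.

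**The concern.** OS is a primary outcome, and two analysts following this text could start its clock on different dates. The choice affects validity as well as labelling. If the clock starts at mRCC diagnosis while membership depends on treatment that comes later, everyone in the analysis is known to survive from diagnosis to treatment. Patients who died in that interval have been removed. A plain Kaplan-Meier curve counts the interval as time at risk, and so do the Cox risk sets. The resulting curve is too high as an account of survival from mRCC diagnosis. The plan mentions no delayed entry, landmark or other device to deal with this.

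**Working it through.** **Step 1. The two readings.** There are two candidate dates, mRCC diagnosis and treatment start. Index is a term that can point to either.

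| Reading | From-diagnosis objective (6.1) | Guaranteed survival in overall OS |
|---|---|---|
| Override in 7.2 governs | Not delivered; overall OS becomes OS from first-line start | None |
| 6.1 and the general index in 7.2 govern | Delivered for OS, against the override | From diagnosis to first treatment |

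Sections 6.1 and 7.7.3 alone could describe two planned analyses. The override in 7.2 blocks that reading. PFS/TTNT has no from-diagnosis version in either row. OS and TTNT by line start at treatment, so they are unaffected in both.

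**Step 2. Size under the from-diagnosis reading.** The plan has no survival or gap figure to reproduce, so every input here is an assumption.

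- Time from mRCC diagnosis to death, D: exponential, rate l = ln 2 / median, with median 12, 18 or 24 months.
- Gap to treatment, G: zero with probability p0 (treatment start is itself an index event), otherwise exponential with rate g = 1 / mean. p0 is 0.3 or 0.5.
- A patient is in the cohort if G < D.

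Survival from diagnosis among the treated:

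S(t) = [p0·e^(−lt) + (1−p0)·(e^(−lt) − (l/(l+g))·e^(−(l+g)t))] / [p0 + (1−p0)·g/(g+l)]

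Middle case (median 18, p0 = 0.3, mean gap 3):

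- l = 0.0385 and g = 0.3333, so g/(g+l) = 0.8964 and l/(l+g) = 0.1036.
- Denominator: 0.3 + 0.7 × 0.8964 = 0.9275.
- At 12 months: e^(−12l) = 0.6300 and e^(−12(l+g)) = 0.0115. Numerator: 0.6300 − 0.7 × 0.1036 × 0.0115 = 0.6291. S(12) = 0.6291 / 0.9275 = 67.8%, against a true 63.0%.
- Solving S(t) = 0.5 gives 19.95 months, an excess of 1.95.

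Excess in median OS, in months, for true medians of 12 / 18 / 24:

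| Mean gap (if not zero) | p0 = 0.3 | p0 = 0.5 |
|---|---|---|
| 0.5 month | 0.34 / 0.35 / 0.35 | 0.24 / 0.25 / 0.25 |
| 1 month | 0.67 / 0.68 / 0.69 | 0.48 / 0.49 / 0.49 |
| 3 months | 1.87 / 1.95 / 1.99 | 1.31 / 1.38 / 1.41 |
| 9 months | 4.03 / 4.78 / 5.20 | 2.66 / 3.26 / 3.60 |

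The direction is always upward. The size depends mainly on the gap.

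**Step 3. IMDC strata under the same reading.** A score of 0 requires at least 12 months from RCC diagnosis to treatment. If mRCC is identified k months after RCC diagnosis, with k < 12, a score-0 patient cannot die in the first 12 − k months from the mRCC index (9 months if k = 3). If k is 12 or more, the factor adds nothing. Patients treated before 12 months score at least 1 and are not in this group. The constraint therefore binds only when mRCC is identified within 12 months and treatment starts at or after 12 months. The documents do not give the number of such patients.

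**Step 4. What delayed entry does.** When the gap is unrelated to prognosis, entering patients at first treatment restores the true median. Two limits remain.

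- *Small early risk sets.* The share of treated patients at risk at time t is e^(−lt)·[p0 + (1−p0)(1 − e^(−gt))] / denominator. At 14 days in the middle case this is about 42 of every 100, or 59 with p0 = 0.5.
- *Partial correction if treatment depends on prognosis.* Assume half the patients are fit and half frail, with medians of 24 and 8 months, 90% and 50% eligible for treatment, p0 = 0.3 and mean gap 3. The median is 13.2 months in all mRCC patients, 18.1 in treated patients counted from diagnosis, and 15.7 with delayed entry.

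**The case against.** **The specific rule should win.** The override in 7.2 is explicit, 7.7.3 is headed Treatment outcomes, and the Study information table lists OS among them. Read that way, index in 7.7.3 means first treatment and there is no guaranteed survival. This is a fair reading, and it rules out a stronger inference that a reader might draw: that the planned OS analysis is biased as it stands. The text does not establish that. The reading still leaves the primary objective in 6.1 without an analysis.

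**The figures are not available.** Figure 1 (study time windows) and Figure 3 (outcome definitions) are not shown and may clarify the origin. The written sections would still need to agree with them.

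**The cohort is openly treated-only.** The stated aim in section 5 concerns "patients with advanced/metastatic RCC treated at the HDSF", so OS from diagnosis could be offered as a description of patients who reach treatment. That is true if it is labelled so. The overstatement is relative to survival from mRCC diagnosis, which is how an unlabelled from-diagnosis curve would be read, and section 7.9 gives no warning.

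**The favourable-risk effect is easy to overstate.** A reader might infer that favourable-risk patients have 100% 12-month survival by construction, or that the effect is largest in that stratum. A reader might also size it from the 20–30% in section 5 "of patients present with metastatic RCC (mRCC) at the time of diagnosis". None of this is supported. That percentage describes all RCC patients, and those treated within a year leave the score-0 group. Section 7.2 also places the index event after the initial RCC diagnosis, so a same-day index may not occur. Only the narrow condition in Step 3 of the working stands.

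**The size is all assumption.** This stands too. The figures show direction and sensitivity and do not estimate the bias in this cohort.

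**Conclusion.** The point holds in conditional form. The inconsistency rests on the text alone: sections 6.1, 7.2 and 7.7.3 allow two origins for overall OS, and no reading delivers every part of the objective. The upward bias follows only if OS is run from mRCC diagnosis in the treated-only cohort by plain Kaplan-Meier or Cox methods. Its size cannot be determined from the documents. Under the assumptions shown it runs from negligible (0.2 to 0.3 months at a mean gap of half a month) to 5.2 months, with 1.95 months in the middle case. On that reading the IMDC strata add guaranteed survival for a limited subgroup of unknown size. This should be fixed before analysis, because the correction is cheap and the outcome is primary.

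**What to change.** State one origin for each analysis and make sections 6.1, 7.2 and 7.7.3, and Figure 3, agree.

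- **Preferred.** Start overall OS at first treatment, and remove the from-diagnosis wording for OS and PFS/TTNT in 6.1. This costs wording changes only.
- **If OS from mRCC diagnosis is kept.** Use delayed entry at first treatment in both the Kaplan-Meier and Cox analyses, for example Surv(time to treatment, time to end, death) in R. Label the result as conditional on treatment. State the two drawbacks: small early risk sets, and only partial correction if treatment depends on prognosis. This needs a small code change and no new data.
- **Optional addition.** Give a descriptive OS from diagnosis in all identified mRCC patients. The untreated are already characterised under the first primary objective. Sections 6, 7.2 and 7.2.2 must then be amended. This analysis can have no IMDC stratification or IMDC covariate, since untreated patients have no treatment-date score, so 7.2.3 needs an exception as well. The identification proxies may miss some untreated patients.
- **In every case.** Show no from-diagnosis OS by IMDC category without delayed entry. Report the distribution of the diagnosis-to-treatment interval, including the share at zero. Add conditioning on treatment to the limitations in 7.9.
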